**j) Withdrawal of Subjects:**

	Protocol Name:	Comprehensive Home-based Self-management Support for COPD Patients
	Principal Investigator:	[name], MPH
	Primary Contact Name/Contact Info:	[name]; [contact]; [contact]
	Date Revised:	4/16/21
	Study Number:	STUDY-18-01345

Procedures for Subjects to Request Withdrawal

Participants that wish to withdraw from the study can do so by contacting the Principal Investigator or research staff. Participants may also withdraw their permission for the use and disclosure of any of their protected information for research, but they must do so in writing to the Principal Investigator. Even if the participant withdraws their permission, the Principal Investigator for the research study may still use the information that was already collected if that information is necessary to complete the research study.

Procedures for Investigator to Withdraw Subjects

The Principal Investigator may stop the participant’s involvement in the research study at any time without their consent. If so, Principal Investigator will communicate the participant of his decision through writing.

**4. Provisions for Research Related Harm/Injury:**

Principal investigators will review all data collection forms on an annual basis for completeness and accuracy of the data as well as protocol compliance. A statement reflecting the results of the review will be sent to the IRB and the sponsor in the annual report.

Adverse event grading

Attribution scale: An adverse event is defined as both an expected side effect that is of a serious nature, or an unexpected side effect/event regardless of severity. All events will be graded as to their attribution (unrelated to protocol, or possibly, probably, or definitely related to protocol).

Any event that is reported to either a principal investigator or their designated research associates by the subject or medical staff caring for the subject and which meets the criteria will be documented as such.

Expected risks: As detailed in the consent form, the expected risk include: Potential risk for loss of private information.

These risks are considered to be minimal and are addressed in the protocol and consent form.

Plan for reporting both anticipated and unanticipated adverse events: All expected and unexpected serious adverse events will be reported according to protocols defined by the NIH. We will expedite reporting of serious adverse events to the IRB, where applicable, when such events are unexpected (within 7 calendar days when life-threatening or fatal; within 15 calendar days for all other unexpected serious adverse events). Copies of reports will be sent to the NIH Project Officer responsible for the study.

The research staff, including project managers and research coordinators, will be trained to identify and report all adverse events, regardless of severity, as well as problems of data security, to the PIs. Weekly study conference calls will involve the MPIs, project managers, and research coordinators. One of the main purposes of the calls will be to ensure patient and study

	Protocol Name:	Comprehensive Home-based Self-management Support for COPD Patients
	Principal Investigator:	[name], MPH
	Primary Contact Name/Contact Info:	[name]; [contact]; [contact]
	Date Revised:	4/16/21
	Study Number:	STUDY-18-01345

safety and ensure compliance with monitoring and reporting. Toward these objectives, every meeting will include: (1) a report of the number and nature of all adverse events occurring during the previous week (monitoring study safety); (2) a discussion of the adverse events and development of a plan or change in study protocol to prevent similar or related adverse events, where possible (minimizing research- associated risk); (3) initiation of the process of reporting adverse events and unanticipated problems to the IRB if they have not yet been reported already (adverse event reporting); (4) identification of breaches of confidentiality of participant data or problems of data security, and discussion and development of plans to prevent problems of data security (ensuring data security). The protocol will be modified as needed to ensure patient safety and data security.

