Research Recruitment and Study Arm Assignment: We will identify potentially eligible patients and will obtain permission from the physician to recruit their patient. We will send a letter to the patient describing the study. One week later, the RA will phone the patient to answer questions and check eligibility of the participant. Eligible patients will be scheduled for an in-person or phone baseline interview, consented and enrolled in the study. We will assess the participant's inhaler technique, electronic medication adherence, and physical activity through a wearable activity monitor. The data from the electronic medication adherence device is for research purposes only. There are no studies demonstrating that providing such data to patients or their doctors improves their medication adherence, thus providing these data to them is unwarranted. The participant will then be randomized to the intervention or control arm.

B.3) SaMBA-COPD Intervention.

	Protocol Name:	Comprehensive Home-based Self-management Support for COPD Patients
	Principal Investigator:	[name], MPH
	Primary Contact Name/Contact Info:	[name]; [contact]; [contact]
	Date Revised:	4/16/21
	Study Number:	STUDY-18-01345

Step 1: Outreach and Engagement. The project manager will notify the CHW supervisor when an eligible and consented patient is randomized to receive care the intervention and will provide the patient's name and contact information (see Description of Procedures Being Performed for recruitment and randomization). The CHW will call the patient within 7 days of consent to schedule a home visit. The CHW will encourage caregivers to join all meetings.

Step 2: Intake. The CHW will perform an intake interview that includes collection of basic information about the patient and their health and healthcare, including medications, intended to enable them to understand their health problems and provide them with chronic illness self-management support.

Step 3: Symptom assessment, medication adherence, and inhaler technique. The CHW will assess the patients' symptoms, adherence to medications, and check inhaler technique following a standardized protocol, and correct errors in inhaler use if identified.

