The clinician will provide supervision of the CHW. This will include reviewing all cases in person or by phone every 7-14 days. Patients will be asked to reduce the intensity of exercise or rest for 5-10 minutes if they develop an uncomfortable level of shortness of breath or fatigue, and to stop exercising if they have symptoms that cause distress or discomfort and do not resolve after rest. Low literacy education methods will be used to ensure their understanding and retention of these instructions. The CHW will maintain communication with the clinician by HIPAA compliant secure email and telephone to report patient performance, trouble shoot problems, and to receive continuing education.

Step 7: Follow-up and Maintenance. The CHW will recommend that meetings occur 1, 4, 8, and 12 weeks after intake and telephone follow-ups weekly through week 8 and monthly thereafter until month 6 when the intervention ends. Calls may be made more often to cognitively impaired patients to enhance information retention. Importantly, the patient and CHW will have the flexibility to tailor the number and frequency of encounters as they see fit. During follow up the CHW will assess patients' progress with SMB, their goals, and their symptoms.

Step 8: Graduation. SaMBA-COPD patients will receive a certificate upon program completion. Description of Procedures Being Performed

a. Patients and Settings. We will recruit patients from the outpatient general medicine and pulmonary practices of Mount Sinai Hospital. Inclusion Criteria: 1) age >40 years; 2) community dwelling; 3) chart-document severe or very severe COPD (FEV1<70% predicted); 4) prescribed any daily medication for COPD; 5) English or Spanish speaking; 6) Smoking history # 10 pack-years; 7) COPD-related ED/hospitalization # 1 visit within the past 12 months. Exclusion Criteria: Diagnosis in the clinical record of dementia, because the study focuses on patients with capacity to independently perform SMB.

	Protocol Name:	Comprehensive Home-based Self-management Support for COPD Patients
	Principal Investigator:	[name], MPH
	Primary Contact Name/Contact Info:	[name]; [contact]; [contact]
	Date Revised:	4/16/21
	Study Number:	STUDY-18-01345

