- Rather than bringing the Principal Investigator or other licensed clinician into the room to meet with the participant in person, the clinician will be contacted via phone and, with the participant's permission, will be given access to join the video conference and conduct an additional assessment via this platform.
- If the clinician determines that that participant is at elevated risk for suicide, the patient is notified by the clinician that 911 will be called and that this will result in an ambulance being sent to their residence to make sure that the subject is okay. The study coordinator remains on the telephone with the patient until the ambulance arrives. The 911 operator is notified if the patient ends the video conferencing call abruptly or hangs up.

	Protocol Name:	Comprehensive Home-based Self-management Support for COPD Patients
	Principal Investigator:	[name], MPH
	Primary Contact Name/Contact Info:	[name]; [contact]; [contact]
	Date Revised:	4/16/21
	Study Number:	STUDY-18-01345

e. Randomization. Randomization will occur immediately after the baseline interview is complete. To obtain the assignment, the RA will access an online program in REDCap that implements the algorithm.

f. Control Arm. The attention control is designed to isolate the impact of screening for self-management barriers, targeted self-management support, and HBEP. The attention control will consist of 3 visits by a CHW to the home to review the COPD education booklet (COPD 1-2-3). During the first visit, this CHW will review the COPD 1-2-3 booklet in its entirety with the patient. During visits 2 and 3, the CHW will make a visit to "check in" with the patient, ask how they are doing with their respiratory symptoms, and review any sections of the COPD 1-2-3 booklet the patient chooses. The CHW will recommend visits every 2 months but the patient and CHW may choose to modify the interval as needed. If the patient appears to be experiencing worsening respiratory symptoms during any visit, the CHW will notify the patient's physician.

g. Quantitative Data Collection. Baseline, 6- and 9-month interviews will be in-person or over the phone in English or Spanish. Bilingual RAs will conduct them at home or in clinical spaces, by patient preference, using laptop computers and REDCap software, as we do with all of our research.

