The DSMB may recommend stopping the trial if there is clear evidence of harm or overwhelming benefit. Adverse events will include disruption of previously established regular care such that the patient's health is jeopardized or excessive burden created by the time required to participate in the study. The study team will monitor and report on self-reported accidents, primary care visits, participants using oxygen therapy, and unanticipated problems to the DSMB. The DSMB can recommend changes in study protocol or termination of the study if it concludes the study design causes disruptions in patient-provider continuity which jeopardized the health of the study subject or if the study imposes excessive burden on patients. Finally, the DSMB, at the request of the sponsor, will review accrual and evaluate study progress towards meeting recruitment targets.

*7. Where applicable, indicate dose selection procedures that will be used to minimize toxicity.*

N/A

*8. List any specialized grading system that will be used to evaluate adverse events (e.g., National Cancer Institute Common Toxicity Criteria).*

N/A

*9. Describe procedures that will be used to assure data accuracy and completeness.*

Additional review of data accuracy by study analyst and statistician. Aggregated data is shown to the DSMB in both closed and open meetings.

*10. Should a temporary or permanent suspension of your study occur, in addition to the PPHS, indicate to whom (NIH, FDA, sponsor, IRB) will you report the occurrence.*

Should a temporary or permanent suspension of the study occur, in addition to the PPHS, we will report this to NIH.

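### No adverse event questioning common to both arms is described, and the intervention arm has about 17 recommended CHW contacts against 3 in control, so by-arm comparisons of non-hospital events are open to ascertainment bias

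*Protocol*

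**What the plan says.** **Capture.** Protocol section 4 documents as an adverse event "Any event that is reported to either a principal investigator or their designated research associates", when it comes from the subject or treating medical staff and meets the definition. The same section has research staff trained to identify and report events, and weekly calls review them. Item 6 of the monitoring plan (section 3.i) adds: "The study team will monitor and report on self-reported accidents, primary care visits, participants using oxygen therapy, and unanticipated problems to the DSMB". Hospital and ED use comes from self-report and SPARCS (section 3.e, description of data to be collected). The outcome and data-collection lists in section 3.e name no adverse event instrument.

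**Contact, intervention arm.** Step 2: "The CHW will perform an intake interview that includes collection of basic information about the patient". Step 7: "The CHW will recommend that meetings occur 1, 4, 8, and 12 weeks after intake", with "telephone follow-ups weekly through week 8 and monthly thereafter until month 6 when the intervention ends". The schedule is not fixed: "the patient and CHW will have the flexibility to tailor the number and frequency of encounters as they see fit".

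**Contact, control arm.** Section 3.e, f: "The attention control will consist of 3 visits by a CHW to the home", and "The CHW will recommend visits every 2 months but the patient and CHW may choose to modify the interval as needed".

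**Common to both arms.** Blinded RAs interview all patients at 6 and 9 months.

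**Use of the data.** The DSMB reviews adverse events alongside hospitalization, mortality and disenrollment (sections 3.h and 3.i). The SAP contains no safety analysis.

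**The concern.** When an event enters the record because someone mentions it, the chance of recording it rises with the number of occasions to mention it. Here those occasions differ between arms by design.

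Their content differs too. Intervention CHWs review symptoms and progress, and exercise cases are discussed with a clinician every 7 to 14 days (Step 6). The control CHW's one written duty when respiratory symptoms worsen is to tell the patient's own physician.

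The events most exposed are those that SPARCS would not show: minor falls, accidents, primary care visits and changes in oxygen use. Only the intervention arm exercises under the study program, so the harm signal of most interest is also the one most affected by closer observation. An excess of such events in that arm could be detection, and a true excess could be explained away as detection. The DSMB may recommend stopping for clear harm, and with 29 patients per arm a few extra recorded events could alter the picture.

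**Working it through.** **1. Contact counts**

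- Control: 6 months at one visit every 2 months = 3, which matches the stated 3.
- Intervention: 1 intake + 4 meetings (weeks 1, 4, 8, 12) + 8 weekly calls + 4 monthly calls (months 3–6) = 17.
- Low count: if a meeting replaces the call due at weeks 1, 4 and 8 and at month 3, 17 − 4 = 13.
- High count: adding the outreach call, exercise evaluation, pharmacist visit and pharmacist call, 17 + 4 = 21.
- With the two shared follow-up interviews: 17 + 2 = 19 against 3 + 2 = 5, a ratio of 3.8. For 13 and 21 the ratios are 15/5 = 3.0 and 23/5 = 4.6.

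**2. Contacts that can surface an event**

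Only contacts after an event can surface it. Assume event times uniform over 9 months. A contact at month c then follows the event with probability c/9, so the mean number of usable contacts is the sum of contact times divided by 9. One week is 12/52 month.

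- Intervention: intake 0; meetings 25 × 12/52 = 5.77; weekly calls 36 × 12/52 = 8.31; monthly calls 3 + 4 + 5 + 6 = 18; interviews 6 + 9 = 15. Sum 47.08, and 47.08/9 = 5.2.
- Control, visits at months 0, 2, 4: (6 + 15)/9 = 2.3.
- Control, visits at months 2, 4, 6: (12 + 15)/9 = 3.0.

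**3. Share of events recorded**

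Let q be the chance that one later contact surfaces the event and puts it on record. The documents do not give q, so it is assumed. With n(t) contacts remaining after time t, the recorded share is the average over t of 1 − (1 − q)^n(t).

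Intervention n(t):

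- weeks 0–8, week by week: 18, 16, 15, 14, 12, 11, 10, 9
- weeks 8–12: 7
- week 12 to month 3: 6
- months 3–4, 4–5, 5–6: 5, 4, 3
- months 6–9: 1

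Control n(t) over months 0–2, 2–4, 4–6 and 6–9: 4, 3, 2, 1 (first visit at month 0) or 5, 4, 3, 1 (first visit at month 2).

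Example, q = 10%:

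- Control, first visit at month 2: [2(0.4095) + 2(0.3439) + 2(0.2710) + 3(0.1)]/9 = 0.261.
- Control, first visit at month 0: [2(0.3439) + 2(0.2710) + 2(0.1900) + 3(0.1)]/9 = 0.212.
- Intervention: 3.275/9 = 0.364.
- Ratios: 0.364/0.261 = 1.4 and 0.364/0.212 = 1.7.

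| Assumed q | Intervention | Control | Apparent ratio, equal true rates |
|---|---|---|---|
| 5% | 22% | 11–14% | 1.5–1.9 |
| 10% | 36% | 21–26% | 1.4–1.7 |
| 20% | 55% | 39–46% | 1.2–1.4 |
| 50% | 81% | 74–79% | 1.03–1.10 |

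With the low count of 13, the sum of times is 47.08 − 13 × 12/52 − 3 = 41.08, or 4.6 usable contacts. The same formula then gives 1.4–1.8, 1.3–1.6 and 1.2–1.4 for q of 5%, 10% and 20%.

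**4. Events with an equal second source**

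If a source common to both arms captures a share s of events, the recorded share is 1 − (1 − s)(1 − q)^k for k CHW contacts. Even crediting all 17 against 3, and with q of 5% to 20%, s = 0.8 gives a ratio of about 1.11, s = 0.95 gives 1.02–1.03, and s = 1 gives 1.00. Hospital and ED use is little affected if SPARCS is nearly complete.

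**The case against.** The case on the other side has real force on several points.

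- **Capture is not purely passive.** Research staff are trained to identify events and weekly calls review them. Self-reported names a source and does not mean unsolicited. The interview questionnaire is not in the documents, so its content cannot be excluded. This stands. What remains is that no common question, form or schedule is described.
- **The reporting route is not written.** Section 4 gives project managers and research coordinators as examples of trained staff. CHWs belong to the study team, but no path from CHW to PI is set out. If no event surfaced by a CHW were passed on, this mechanism would produce no difference. That limits the claim and is itself a gap.
- **A by-arm DSMB table is not stated.** A reader might infer that the DSMB receives a biased arm comparison. The monitoring plan says only that aggregated data are shown in closed and open meetings. Judging harm from the intervention would naturally involve comparing arms, but that is an inference. Hospitalization and mortality, first on the DSMB's list, are the least exposed items.
- **The raw counts overstate the effect.** A reader might take the nearly sixfold difference in CHW contacts (17/3 = 5.7) as the size of the bias, or apply 1 − (1 − q)^k to 19 and 5 contacts and get ratios of 2.8, 2.1 and 1.5. The first leaves out the shared interviews. The second credits contacts held before the event, and the intervention contacts are front-loaded. The schedule is also flexible in both arms.

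The design imbalance survives all of this: no reading of the recommended schedules brings the arms close.

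**Conclusion.** The point holds as a risk, not as a demonstrated bias. For non-hospital events the plan does not specify equal ascertainment, and contact is unequal by design, so a by-arm difference in recorded events could not be separated from closer observation. With equal true rates, the apparent ratio is about 1.5–1.9, 1.4–1.7 or 1.2–1.4 at an assumed 5%, 10% or 20% chance per later contact, and close to 1 for events that most contacts would bring out.

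These figures assume the recommended schedules are followed, event times are uniform over 9 months, every contact (interviews included) has the same chance of surfacing an event, and CHW-surfaced events reach the PI. The documents do not support reading this as a fault in hospital and ED data, or as a finding that the DSMB was shown a distorted comparison. The change is worth making because it is cheap and because nothing in the SAP would correct the imbalance later.

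**What to change.** 1. Have the blinded RAs ask the same short adverse event checklist in both arms at the existing 6- and 9-month interviews, covering at least falls, accidents, primary care visits and oxygen use.
2. State in the SAP that by-arm safety comparisons rest on those answers plus SPARCS.
3. Tabulate events surfaced at CHW, pharmacist or clinician contacts separately by source. They still go to the PI and the DSMB, but are not the primary comparison between arms.
4. Write down how a CHW in either arm passes an event to the PI.

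The cost is a slightly longer interview, one more breakdown in the safety tables and a short procedural text. The downside is recall over 6 months at the first interview and 3 months at the second, which will miss some minor events but applies equally to both arms.

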## 5. Recordings:

- *Will any video or audio recordings be made for research purposes? If so please describe:* Audio recordings will be conducted for qualitative interviews of participants for phase 1. Within phase 2, participants may also be contacted to participate in an optional exit interview. This audio/video recorded interview will gather information on the participant’s experience in the randomized controlled trial and obtain qualitative data on the RCT’s facilitators and barriers to program implementation.

- *How will the data be recorded, transmitted and stored, keeping in mind that this is likely PHI and should be encrypted, etc.?*

Recorded files will be encrypted and password protected. They will be stored in a folder on the shared network drive for the Division of which only those on the study have access. Each file will be identified by a code. All identifying information will be removed.

- *How long will the data be held?*

The data will be held for 12 months after the participant completed the recording.

- *Is this an optional part of the project, and if not, what is the scientific need to compel people to be recorded in order to participate in the research?*

The phase 1 qualitative research is not optional. If a participant volunteer chooses to participate and consent to the research, they would be audio/video recorded. The recording is necessary to interpret the qualitative analysis in order to refine the phase 2 pilot, proposed in the original grant submission.

The exit interview is optional.

- *How can subjects ask to have the recordings and transcripts destroyed?*

The participant can request to have their recording and/or transcript destroyed at anytime throughout the study and we will not use them in the research. They can call, mail or email our research team to request to have their recording data destroyed.

	Protocol Name:	Comprehensive Home-based Self-management Support for COPD Patients
	Principal Investigator:	[name], MPH
	Primary Contact Name/Contact Info:	[name]; [contact]; [contact]
	Date Revised:	4/16/21
	Study Number:	STUDY-18-01345

